5.2 Reporting procedures

All adverse events should be reported. Depending on the nature of the event the reporting procedures below should be followed. Any questions concerning adverse event reporting should be directed to the Chief Investigator in the first instance.

5.2.1 Non serious AEs

All such events, whether expected or not, should be recorded- it should be specified if only some non-serious AEs will be recorded, any reporting should be consistent with the purpose of trial end points.

5.2.2 Serious AEs

An SAE form should be completed and emailed to the Chief Investigator within 24 hours. However, hospitalisations for elective treatment of a pre-existing condition do not need reporting as SAEs.

All SAEs should be reported to the Bromley Research Ethics Committee ([contact]) where in the opinion of the Chief Investigator, the event was:

- 'related', ie resulted from the administration of any of the research procedures; and
- 'unexpected', i.e., an event that is not listed in the protocol as an expected occurrence

Reports of related and unexpected SAEs should be submitted within 15 days of the Chief Investigator becoming aware of the event, using the NRES SAE form for non-IMP studies. The Chief Investigator must also notify the Sponsor of all SAEs.

Local investigators should report any SAEs as required by their Local Research Ethics Committee, Sponsor and/or Research & Development Office.

Contact details for reporting SAEs

[contact]

CI email (and contact details below)

Please send SAE forms to: [contact] and Cc [contact]

[contact] (Mon to Fri 09.00 – 17.00)

6. Regulatory issues

6.1 Ethics approval

The Principal Investigator has obtained approval from the Health Research Authority via the Bromley Research Ethics Committee. The study will be conducted in accordance with the recommendations for physicians involved in research on human subjects adopted by the 18th World Medical Assembly, Helsinki 1964 and later revisions.

6.2 Consent

Consent to enter the study will be sought from each participant only after a full explanation has been given, a patient information sheet offered, and time allowed for consideration. Signed participant consent will be obtained. The right of the participant to refuse to participate without giving reasons will be respected. All participants are free to withdraw at any time.

6.3 Confidentiality

The Principal Investigator will preserve the confidentiality of participants taking part in the study and fulfil transparency requirements under the General Data Protection Regulation for health and care research. Data and all appropriate documentation will be stored for a minimum of 10 years after the completion of the study, including the follow-up period.

6.4 Indemnity

Imperial College London holds negligent harm insurance policies which apply to this study.

6.5 Sponsor

Imperial College London will act as the main sponsor for this study.

6.6 Funding

Imperial College London (ICL) are funded through the Discover-NOW Health Data Research Hub, of which Imperial College Health Partners (ICHP) are lead partner and Imperial College London are an academic partner. Discover-NOW is funded by a grant from the UK Research and Innovation (UKRI) Industrial Strategy Challenge Fund (ISCF). Partial additional funding for the study (i.e., additional to the Hub grant funding) has been provided directly by ICHP.

We expect Imperial College London's research study budget to be 135,000 GBP based on the activities and approach outlined above. The study's funding is covered under the terms of the Consortium Agreement relating the Discover-NOW Digital Innovation Hub entered into between Imperial College of Science, Technology and Medicine and ICHP effective 20 November 2019.

This consortium was formed in connection with the Parties' successful application in response to the Digital Innovation Hub Prospectus issued by the Medical Research Council (MRC) on behalf of UK Research and Innovation (UKRI), working together with Health Data Research UK Limited (HDRUK), for funding through the Industrial Strategy Challenge Fund (ISCF).

[figure not shown]
6.7 Audits

The study may be subject to inspection and audit by Imperial College London under their remit as sponsor.

7. Publication policy

The Investigators and representatives of the collaborating organisations will be involved in reviewing drafts of the manuscripts, abstracts, press releases and any other publications arising from the study. Authors will acknowledge that the study funding as detailed in Section 6.6 above. Authorship will be determined in accordance with the ICMJE guidelines and other contributors will be acknowledged.

Appendix 1: Fresh Start overview

Appendix 2: Overview of study procedures

Step									
	Patient search	Outreach, Qualification & Booking	Onboard	Know Diabetes Emails	Huma App and Devices	Virtual Group Consultations (VGC)	Before	During	
Staff actions at primary care practice	Run EPR search report to find list of patients.	Contact patients by phone, invite them to the service and ensure they can participate.	Run virtual appointment or phone call to onboard patient onto the service.	Sign the patient up by email and make sure they are receiving emails OK.	Check Huma clinician dashboard daily for safety (red flags) and to see whether patients are using app.	Look at Huma dashboard, move some key data into EPR.	Run VGC session with 6-10 patients.	Internally discuss notes and actions from VGC after session.	Decide whether to discharge patient, repeat service for 12-weeks or escalate them to an MDT for further support.
		Book them onto a formal onboarding appointment and book bloods if missing.	Provide Huma app, book 3 x VGC sessions, sign up for Know Diabetes emails, answer questions		Escalate care if red flag spotted.	Fill out VGC "discussion board" slide and agree talking points for VGC session.	Review and discuss patient goals and clinical metrics.	Refer to clinical protocols; agree and action any required care plan and treatment changes or referrals.	
		Book to collect devices.	Patient collects devices from practice.		Patients set their own goals.	Identify and note clinical treatment or care plan changes and referrals required.	Discuss possible clinical and care plan decisions.		
How long it should take?	5m total	10m per patient	30m-45m per patient	1m per patient	1-2m per patient	1hr total	1hr15m total	1hr total	1hr total
How often it should be done?	Once, at beginning of 12 weeks	Once, at beginning of 12 weeks	Once, at beginning of 12 weeks	Twice, at beginning and at first VGC session	Daily	Before each VGC	During each VGC	After each VGC	Once, at end of 12 weeks

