3.7 Study procedures

This section provides detail on the procedures for delivering Fresh Start and data collection. Standard operating procedure (SOP) documents that go into greater detail have been developed for staff at primary care practices who will be delivering Fresh Start. These include SOPs for practice nurses (PNs), healthcare assistants (HCAs), and administrative staff. A training document has also been developed for participating primary care practices.

The below are the main steps involved to deliver Fresh Start. A high-level overview of study procedures is also provided at Appendix 2.

- Patient search
- Outreach, qualification and booking
- Onboarding
- Fresh Start educational emails
- Huma app, devices and clinician dashboard
- Video group consultations (VGCs)
- Discharge, repeat, or MDT escalation
- Interviews with patients and healthcare professionals
- Online System Usability Scale (SUS) survey

Patient search

EPR searches have been constructed based on the inclusion criteria for this study (see Section 4.3). This search will be run by administrative staff at participating primary care practices. Patients will then be invited to participate in the program.

Staff actions at primary care practice:

- Open practice management system and run report search
- Sense-check list of patients against risk stratification criteria
- Mark exported patients to receive outreach invitation to service

Outreach, qualification and booking

Outreach will involve a 10-minute initial conversation with patients identified in the search to speak to them about how Fresh Start may help them, find out if they are able to participate, and, if interested, book them onto the required appointments to start on Fresh Start. The participant must be able to download the Huma App to their smartphone or tablet.

Staff actions at primary care practice:

- Phone patients on the outreach list
- Qualify if patients are eligible for service
- Organise device collection from the practice
- Book patient onto onboarding appointment
- Keep track of the uptake of Fresh Start
- Book patient for **baseline measurements**, which will include:
 - HbA1c
 - Lipid panel
 - Weight

Onboarding

Imperial College London

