4.3 Inclusion criteria

- Patients over the age of 18 with the capacity to give consent
- Patients with 'high risk' OR 'very high risk' T2DM as defined by:
- **Very high risk - T2DM with existing ASCVD OR T2DM without ASCVD but with any 3 of the following:**
 - HbA1c >58 mmol/mol
 - SBP >140 mm Hg
 - Non-HDL >3.35 mmol/L or LDL-C >2.5 mmol/L
 - Nephropathy (eGFR <45 ml/min, or Urine ACR >3 mg/mol)
 - Retinopathy
 - Neuropathy (including moderate/high risk feet, previous foot ulceration and erectile dysfunction)
 - Currently smoking
- **High risk - T2DM without ASCVD but with any 2 of the following:**
 - HbA1c > 58 mmol/mol
 - SBP >140 mm Hg
 - Non-HDL >3.35 mmol/L or LDL-C >2.5 mmol/L
 - Nephropathy: eGFR <45 ml/min or Urine ACR >3 mg/mol
 - Retinopathy

- Neuropathy (including moderate/high risk feet, previous foot ulceration and erectile dysfunction)
- Currently smoking
- Black, Asian and minority ethic (BAME) status

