6.3. Secondary Analysis Variables

6.3.1. Safety of Fresh Start

Safety is to be determined by the following as entered in study dataset over the 12-week assessment period:

- Number of deaths
- Number of emergency department admissions
- Number of hospital admissions

6.3.2. Impact of Fresh Start on clinical outcomes.

To evaluate the impact of Fresh Start on clinical outcomes the following outcomes will be assessed:

- HbA1c, recorded via patient records at baseline, upon completion of 12-week assessment period and at 6 months
- Lipids, incl. LDL and non-HDL cholesterol, recorded via patient records at baseline, upon completion of 12-week assessment period and at 6 months
- Weight, recorded via patient records at baseline, upon completion of 12-week assessment period and at 6 months
- Diabetes Distress Scale score (DDS), as recorded within HUMA once monthly across the 12-week assessment period and also at 6 months
- Blood glucose time-in-range, as recorded within HUMA over the 12-week assessment period

Time-in-range is to be defined as the percentage of time that a participant spends with their blood glucose levels between 70 to 180 mg/dl.

- Systolic blood pressure (SBP), as recorded within HUMA, as recorded within HUMA over the 12-week assessment period

7. Statistical Methodology

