7.6. Secondary Analysis Methodology

7.6.1. Safety of Fresh Start

From the safety parameters established in 6.3.1, safety of Fresh Start is to be assessed via the following over 6 months:

- Number of deaths

Number of deaths is to be presented by frequency per group.

- Number of emergency department admissions

Number of patients with emergency admissions is to be presented by frequency per group

- Number of hospital admissions

Frequency of events per patient is to be presented in a frequency table by treatment group with percentages to 1 dp.

Number of patients with hospital admissions is to be presented by frequency per group

Statistical comparison of safety will consist of a composite outcome, including all three events listed above. Number of patients with a safety event occurring is to be presented by frequency per group with difference in number of patients presented with a 95% CI.

7.6.2. Impact of Fresh Start on clinical outcomes.

From the clinical outcome parameters established in 6.3.2, potential efficacy of Fresh Start is to be assessed via the following

- **HbA1c, at baseline, 12-week and at 6 months**
- **Lipids, at baseline, 12-week and at 6 months**
- **Weight, at baseline, 12-week and at 6 months**

Tables displaying summary statistics will be produced displaying mean, SD, median, minimum & maximum at timepoints BL, W12 & M6

Within-group change from baseline at 12 weeks will be assessed via a mixed-effects model taking values at 12-weeks as the dependant variable and adjusting for covariates; baseline, sex, age, social deprivation index and allowing for clustering by GP Practice

Between-group differences in change from baseline at 12 weeks will be analysed using a similar mixed-effects model including an additional parameter for treatment effect and again adjusting for covariates; baseline, sex, age, social deprivation index and allowing for clustering by GP Practice

Further analysis will take place once long-term (6-month) follow-up is completed using an adjusted version of the above models containing additional terms for visit and visit*treatment interaction.

- **Diabetes Distress Scale score (DDS), as recorded within HUMA once monthly across the 12-week assessment period and also at 6 months**

Summary statistics displaying mean, SD, median, minimum & maximum DDS will be produced at for first reading and last reading.

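### The plan conflicts on whether baseline bloods are taken afresh, so the eligibility HbA1c or lipid value can serve as baseline and could bias the within-group change toward improvement

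*Protocol*

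**What the plan says.** Protocol 3.7, under outreach and booking, gives an unconditional instruction: "Book patient for baseline measurements, which will include" HbA1c, a lipid panel and weight. The overview table in Protocol Appendix 2 makes the blood tests conditional: "Book them onto a formal onboarding appointment and book bloods if missing". SAP 5.7 repeats that table with the same wording. Neither document says what counts as missing.

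Patients are found from values already on record: "EPR searches have been constructed based on the inclusion criteria for this study" (Protocol 3.7). The criteria in Protocol 4.3 include "HbA1c >58 mmol/mol" and "Non-HDL >3.35 mmol/L or LDL-C >2.5 mmol/L". Neither is sufficient alone. Very high risk means "T2DM with existing ASCVD OR T2DM without ASCVD but with any 3 of the following"; high risk without ASCVD needs two factors, from a list that also counts BAME status.

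SAP 6.3.2 defines the outcome as "HbA1c, recorded via patient records at baseline, upon completion of 12-week assessment period and at 6 months", with parallel wording for lipids. It gives no date window and does not bar the value that the search read. SAP 7.6.2 then states: "Within-group change from baseline at 12 weeks will be assessed via a mixed-effects model taking values at 12-weeks as the dependant variable", adjusting for baseline, sex, age and deprivation. A between-group model adds a treatment term. The only explicit baseline rule in SAP 7.6.2 is for the fallback blood glucose analysis, which takes the first reading.

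**The concern.** A patient flagged by the search on HbA1c or lipids has, by definition, that result on record. Under the conditional wording no new sample is needed, so the qualifying result can become the baseline. A value that admits a patient because it was high tends to be lower on repeat with no intervention at all, and the 12-week value is such a repeat.

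Adjusting for baseline does not remove this from a single-group change. At the mean baseline the fitted 12-week value is the mean 12-week value, so the estimated change is still the raw mean difference.

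The pre-test/post-test comparison is a named design element (Protocol 3.1, SAP 5.1), and Protocol section 2 says the results may support continuing the service. A small drift toward improvement in an uncontrolled change could therefore be read as benefit.

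**Working it through.** The plan states no figure for this point, so there is none to reproduce. The size is illustrated from the entry rule plus assumptions.

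**From the documents:** HbA1c threshold 58 mmol/mol; non-HDL threshold 3.35 mmol/L; entry by ASCVD or at least two listed factors, with seven factors besides HbA1c in the high-risk list; at least 300 participants; 10 practices; ICC 0.05.

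**Assumed, because the documents give nothing:** HbA1c normal with mean 55–60 and SD 12–18; repeat correlation r 0.7–0.9; ASCVD prevalence A 15–30%; on average 1.0–2.6 of the seven other factors per patient, equally likely and independent; no treatment effect; every recorded value used as baseline (the worst case).

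**Step 1: fall among patients selected on HbA1c above 58.**

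Fall = (1 − r) × SD × φ(a) / (1 − Φ(a)), with a = (58 − mean)/SD.

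- Central case (mean 58, SD 15, r 0.8): a = 0, so 0.2 × 15 × 0.3989 / 0.5 = 2.39 mmol/mol. A simulation gives 2.40 with the qualifying value as baseline and 0.00 with a fresh one.
- Smallest (60, 12, 0.9): 0.83. Largest (55, 18, 0.7): 4.90.
- The same formula for non-HDL above 3.35 mmol/L (assumed mean 3.0–3.4, SD 0.9–1.1, r 0.6–0.9) gives 0.07 to 0.44 mmol/L among those selected on it.

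**Step 2: share of entrants for whom HbA1c was decisive.** Patients with ASCVD or two other factors enter whatever their HbA1c. Among them, high values drift down, low values drift up, and the mean artefact is zero. HbA1c decides entry only with no ASCVD and exactly one other factor. Let p = P(HbA1c > 58), p1 = P(exactly one other factor) and p2 = P(two or more others):

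d = (1 − A) × p1 × p / [A + (1 − A) × (p2 + p1 × p)].

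Example with A = 0.15 and 1.4 other factors (probability 0.2 each): p1 = 7 × 0.2 × 0.8⁶ = 0.367; p2 = 1 − 0.8⁷ − 0.367 = 0.423; p = 0.5. The numerator is 0.85 × 0.367 × 0.5 = 0.156, the denominator is 0.15 + 0.85 × (0.423 + 0.1835) = 0.666, and d = 0.234.

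**Step 3: whole-group fall = d × Step 1.** In the example, 0.234 × 2.39 = 0.56. Simulating the entry rule gives the same 0.56, with 0.00 among entrants for whom HbA1c was not decisive.

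Central case, d and whole-group fall (mmol/mol):

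| Mean other factors | A = 15% | A = 30% |
|---|---|---|
| 1.0 | 0.311; 0.74 | 0.223; 0.53 |
| 1.4 | 0.234; 0.56 | 0.177; 0.42 |
| 2.1 | 0.127; 0.30 | 0.101; 0.24 |
| 2.6 | 0.076; 0.18 | 0.061; 0.15 |

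Over all assumed ranges, the smallest is 0.069 × 0.83 = 0.06 (60, 12, 0.9; A 30%; 2.6 factors) and the largest is 0.281 × 4.90 = 1.38 (55, 18, 0.7; A 15%; 1.0 factor). That is roughly 0.05 to 1.4.

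**Step 4: against precision.** The SD of the change is about SD × √(2(1 − r)). In the central case that is 15 × √0.4 = 9.49, so the 95% half-width with 300 patients is 1.96 × 9.49/√300 = 1.07. Borrowing the ICC of 0.05 from the enrolment calculation, with 300/10 = 30 per practice, the design effect is 1 + 29 × 0.05 = 2.45 and the half-width is 1.07 × √2.45 = 1.68. For the largest fall, the SD is 18 × √0.6 = 13.94 and the half-widths are 1.58 and 2.47. The expected artefact is below the half-width in both cases.

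**The case against.** Section 3.7 is the detailed procedure and itself describes Appendix 2 as a high-level overview. The conditional phrase may mean only that the baseline bloods have not yet been done. The documents do not show that qualifying values will be used, only that nothing prevents it. This stands as a reason to write could rather than would. It does not settle the conflict, because SAP 5.7 carries only the conditional version, as its schedule of procedures, and a recent qualifying value regresses too.

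A reader might infer that the study will show improvement even if the service does nothing, or that 0.8 to 4.9 mmol/mol is the bias in the reported result. The documents support neither. HbA1c above 58 admits nobody on its own, SAP 7.6.2 analyses the whole group, and only decisive cases contribute net bias. Nor does the artefact by itself carry the expected interval off zero in the cases checked.

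A reader might also blame the conflict for baseline dates differing between arms. They would differ under Protocol 3.7 as well, since controls come from routine WSIC records with no scheduled baseline.

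The outcomes are exploratory, and a baseline-adjusted comparison with matched controls is planned. Both limit the consequence. The comparison does not repair the within-group estimate. Between groups the artefact cancels only if controls are selected and dated alike, which is not assured: the propensity score in SAP 7.1.2 omits the risk category that Protocol 3.5 includes.

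**Conclusion.** The contradiction is real and unresolved in the current text, and baseline is undated. If the conditional wording is followed, the within-group change in HbA1c and lipids could be biased toward improvement. Weight is not a selection criterion and is not affected by this mechanism.

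The bias in the whole-group HbA1c change is modest: about 0.15 to 0.7 mmol/mol in the central case and roughly 0.05 to 1.4 over the assumed ranges. These figures rest on normality, independent factors and every recorded value being used as baseline. Fresh samples for some participants would reduce them; correlated risk factors could move them either way. No whole-group figure is offered for lipids, where the same dilution applies. Given the exploratory status, this is a point that should be corrected, not one that undermines the study.

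**What to change.** 1. Reconcile Protocol 3.7 with Protocol Appendix 2 and SAP 5.7 so that all three say the same thing about baseline bloods, and define missing if the word is kept.
2. In SAP 7.6.2, define the participants' baseline for HbA1c and lipids as a value dated after the risk-stratification search and before the first VGC.
3. Flag and count, separately for HbA1c and lipids, participants whose only available baseline is the value the search read. Report the within-group change with and without them. Set the flag by date, not by whether the value exceeds the threshold: dropping only high recorded values would leave low ones that drift up.
4. For controls, state how baseline is dated relative to the index date and report the dating difference between arms. Do not exclude controls who have only routine records; a narrow window there could remove many.

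The cost is wording in two documents, a date check and one extra run of each within-group model. The analysis restricted to fresh baselines will be smaller, possibly much smaller if practices followed the conditional wording, and may then represent a different mix of patients. That is why both versions should be shown.

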7.5.2. Usability of Fresh Start amongst people with 'high risk' or 'very high risk' type 2 diabetes.	19

Imperial Clinical Trials Unit	SUB-STUDY SAP TEMPLATE – SUB-ANALYSES AND OBSERVATIONAL STUDIES	SOP_TEM_BS002
-------------------------------	---	---------------

7.5.3.	Acceptability of Fresh Start amongst people with 'high risk' or 'very high risk' type 2 diabetes.	20
7.5.4.	Acceptability of Fresh Start amongst HCPs	20
7.5.5.	Cost-effectiveness of delivering Fresh Start	20
7.6.	Secondary Analysis Methodology	21
7.6.1.	Safety of Fresh Start	21
7.6.2.	Impact of Fresh Start on clinical outcomes.	22
7.7.	Exploratory / Sub-group Analysis	23
8.	Missing Data	23
9.	SAP Revisions	23

2. Abbreviations

ASCVD	Atherosclerotic Cardiovascular Disease
BP	Blood Pressure
CCG	Clinical Commissioning Groups
CRG	Clinical Risk Groups
DDS	Diabetes Distress Score
DP	Decimal Place
EPR	Electronic Patient Record
GP	General Practitioner
HCA	Healthcare Assistant
HCP	Healthcare Providers
NWL	North-West London
PN	Practice Nurse
PSM	Propensity Score Matching
SAP	Statistical Analysis Plan
SD	Standard Deviation
SUS	System Useability Scale
T2DM	Type II Diabetes Mellitus
VGC	Video Group Consultation
WSIC	Whole of Systems Integrated Care

3. Introduction & Study Summary

As the prevalence of Type 2 Diabetes Mellitus (T2DM) grows the burden on healthcare is increasing in the form of additional consultations, hospital outpatient visits, death and disability. T2DM represents a large part of the disease and cost burden of healthcare in North West London (NWL) to the value of £600m annually. Patients with T2DM constitute over 40% of all NWL admissions, with complications of type 2 diabetes representing a significant factor in the morbidity and cost associated with this chronic disease. To this end, there is an urgent need for healthcare professionals to provide the same or better care without increasing healthcare expenditure. Digital interventions/ healthcare solutions may provide an opportunity to achieve these goals.

The Type 2 Diabetes Exemplar Programme has designed the Fresh Start service for use in primary care to demonstrate how real-world data and technology can improve health outcomes for T2DM patients. Fresh Start has been designed by the Discover-NOW Health Data Research Hub in a cross-industry collaboration between North-West London CCGs, NHSX, AstraZeneca, Imperial College Health Partners and Huma. Fresh Start is offered to patients at high risk of developing complications from T2DM and combines video group consultations, a remote monitoring solution, and educational content.

Fresh Start seeks to support population stratification and strengthen population health management by providing better-tailored services and proactive interventions, particularly among population groups more at risk of the adverse impacts of COVID-19. Mortality risk from COVID-19 is approximately 25% higher in patients with T2DM and shielding has resulted in reduced primary care appointments for patients with T2DM. This has created an immediate need for primary care to adapt and provide remote care pathways to patients. Digital-first remote pathways could make care more accessible while finding time and cost efficiencies. By combining remote monitoring and video group consultations, we can inform the patient-clinician conversation making remote care in group settings safer, efficient and more personalised.

It is our opinion that generating credible evidence for digital health solutions remains an industry-wide challenge, hindering widespread adoption, and that traditional approaches present limitations for researchers to create evidence. Evaluation of digital health solutions has also been identified as requiring improvement and has been cited as a major obstacle for wider adoption. This study will use pragmatic methods to evaluate Fresh Start, with a view to support successful adoption of Fresh Start in primary care practices in the UK.

4. Study Objectives

